13.3.1. Procedures for Sciatic Nerve Block

A: Placement of ultrasound probe:

- Position the patient supine (with the leg placed on an elevated footrest) or lateral (operative side up). Place ultrasound probe in the popliteal fossa, 3 to 5 cm above the popliteal crease in the transverse orientation.
- Identify the sciatic nerve where it splits into the peroneal and tibial nerves but still enclosed in the connective tissue sheath (paraneural sheath).

B: Insertion of needle into paraneural sheath:

- Use a 100 mm, 21-gauge insulated needle
- Needle approach is from the lateral side
- The needle should be advanced in plane until the needle tip has pierced the sciatic nerve sheath (paraneural sheath), (i.e., advance needle underneath the peroneal nerve, and pop through the sheath that surrounds the tibial and peroneal nerves).

C: Hydrodissection of sciatic nerve block:

- Never advance the needle tip directly at either nerve, but rather use small aliquots of saline (1-2 ml) to hydrodissect and outline the nerves.

D: Study drug administration:

- Switch syringes and inject 20 mL of the study drug admixture in the sheath, between the two nerves.

13.3.2. Procedures for Adductor Canal Nerve Block

A: Placement of ultrasound probe:

- With the patient in the supine position, place ultrasound transducer at the midpoint between the inguinal crease and the superior pole of the patella. The femoral artery should be visible directly beneath the sartorius muscle.
- The saphenous nerve is frequently visible as a hyperechoic structure immediately lateral to the femoral artery.

B: Insertion of needle into adductor canal:

- From a lateral approach in plane using a 100 mm 21-gauge insulated needle, insert the needle until the tip is just lateral to the femoral artery and under the saphenous nerve.
- The injection will occur immediately lateral to the femoral artery, below the sartorius muscle.

C: Saline injection of adductor canal nerve block:

- Slowly start the saline injection to visualize the saphenous nerve so as not to injure it. The goal is to confirm needle tip position, and no more than 1-2 mL of saline should be required.

D: Study drug administration:

- Switch syringes and slowly start injecting the remaining 20 mL of study drug around the saphenous nerve as visualized during saline injection.

13.4. Post-Block Assessments

The following assessments will be conducted in Cohort 1 subjects only:

- Assess sensory and motor function (onset and offset of block)

- Perform sensory/motor function assessments at 15 min (± 5 min), 30 min (± 5 min), 45 min (± 5 min), 1 h (± 15 min), 2 h (± 30 min), 8 h (± 30 min), 12 h (± 30 min), 24 h (± 1 h), 30 h (± 1 h), 48 h (± 1 h), 60 h (± 2 h), 72 h (± 2 h), 84 h (± 2 h), 96 h (± 3 h), 120 h (± 3 h), 144 h (± 3 h), and 168 h (± 3 h) from the end of the block procedure, or until full sensory/motor function has returned to predose levels in two consecutive evaluations. The light touch, cold sensation, and motor function tests will be rated independently from each other. For sensory function, the light touch assessment will be done first, followed by the cold sensation assessment.
- Collect scheduled PK blood samples. These samples will be obtained at predose (up to 15 min before block), and at 30 min (± 5 min), 45 min (± 5 min), 1 h (± 15 min), 2 h (± 30 min), 8 h (± 30 min), 12 h (± 30 min), 24 h (± 1 h), 30 h (± 1 h), 48 h (± 1 h), 60 h (± 2 h), 72 h (± 2 h), 84 h (± 2 h), 96 h (± 3 h), 120 h (± 3 h), 144 h (± 3 h), and 168 h (± 3 h) from end of block procedure. (See [Table 2](#)).

In both Cohort 1 and Cohort 2 subjects:

- Record AEs/ SAEs
- Record any concomitant medications for treatment(s) for the events.

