8. Breakthrough pain medication will be provided on a PRN basis in relation to the breakthrough pain intensity. Opioids should not be the first choice for pain relief, unless clinically indicated in the opinion of the Investigator, and should not be given on a schedule.
9. For the initial treatment of post-surgical pain, subjects may receive acetaminophen or NSAIDs without exceeding the maximum daily dose. If the initial pain treatment (acetaminophen or NSAIDs) is insufficient for pain relief, immediate release PO oxycodone may be offered in a stepwise approach: initial dose of 5 mg oxycodone will be offered; if the initial opioid dose is insufficient for pain relief, 10 mg oxycodone may be offered. If a subject is unable to tolerate PO medication or the PO oxycodone pain relief is insufficient, IV morphine (initiated at 2 mg) or hydromorphone (initiated at 0.2 mg) may be administered.

Table 2: Pharmacokinetic and Pharmacodynamic Assessments (Cohort 1 bunionectomy subjects only)

Time Window		Post-study Drug Administration ^a																
		Day of Study Drug Administration to Post-operative Day 4 (POD 4)														POD 5	POD 6	POD 7
		15m	30m	45m	1h	2h	8h	12h	24h	30h	48h	60h	72h	84h	96h	120h	144h	168h
Up to 15 mins before blocks	±5m	±5m	±5m	±15m	±30m	±30m	±30m	±1h	±1h	±1h	±2h	±2h	±2h	±3h	±3h	±3h	±3h	
Collect PK blood sample; Record date and time of blood sample	X		X	X	X	X	X	X	X	X	X	X	X	X	X	X	X	X
Assess and record sensory and motor function ^{b,c}	X	X	X	X	X	X	X	X	X	X	X	X	X	X	X	X	X	X

Abbreviations: h=hour; m=minute; PK=pharmacokinetic

- a. All timepoints are from end of block administration.
- b. Once offset of sensory and motor block are determined (in two consecutive evaluations), no subsequent assessments will be conducted. Sensory and motor are assessed independently.
- c. When subject is in surgery, no sensory or motor block assessments be conducted.

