Duration of sensory block will be defined as the time between onset and offset of light touch sensory and/or cold sensation block for each nerve individually (see Appendix 4, [Section 18.4](#)).

Assessment of motor function (onset and offset of motor block):

- Motor function (onset and offset of motor block) will be assessed by voluntary active movement of the foot. This will be used to determine the onset and duration of motor blockade. The motor function test will be performed at predose (up to 15 min before block), 15 min (± 5 min), 30 min (± 5 min), 45 min (± 5 min), 1 h (± 15 min), 2 h (± 30 min), 8 h (± 30 min), 12 h (± 30 min), 24 h (± 1 h), 30 h (± 1 h), 48 h (± 1 h), 60 h (± 2 h), 72 h (± 2 h), 84 h (± 2 h), 96 h (± 3 h), 120 h (± 3 h), 144 h (± 3 h), and 168 h (± 3 h) from end of block procedure, or until full motor function has returned to predose levels in two consecutive evaluations. Additional unscheduled assessments may be performed, particularly around the surgery, if no onset of block is noted on the last scheduled assessment prior to surgery.

Onset of motor block (sciatic) will be defined as the earliest timepoint with partial or no foot movement.

Offset of motor block (sciatic) will be defined as resolution of the motor block with complete foot movement on two consecutive assessments. After offset of motor block is noted (on 2 consecutive assessments), no subsequent assessments will be conducted.

Duration of motor block will be defined as time between onset and offset of motor block (see Appendix 3, [Section 18.3](#)).

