6.3. Pharmacodynamic Assessments (Cohort 1 only)

Time of onset/offset is collected on the corresponding "PD Assessment – Onset/Offset Sensory/Motor Block" eCRF.

6.3.1. Assessment of Sensory Block:

Sensory function for the sciatic and saphenous nerve will be assessed independently using a wooden tongue depressor and ice. This assessment will evaluate light touch and cold sensation.

Sensory function assessment will include the following four locations:

- 1. Saphenous proximal Medial aspect of the lower leg (3-4 cm below the knee)
- 2. Saphenous distal Medial aspect of the lower leg (3-4 cm above ankle)
- 3. Sciatic proximal Lateral aspect of the lower leg (3-4 cm above ankle)
- 4. Sciatic distal Sole of the foot

The tongue depressor application and ice will be performed at predose, 15 min, 30 min, 45 min, 1 h, 2 h, 8 h, 12 h, 24 h, 30 h, 48 h, 60 h, 72 h, 84 h, 96 h, 120 h, 144 h, and 168 h hours from the end of the nerve block procedure, or until full sensory function has returned to baseline (preblock) levels in two consecutive evaluations. Additional unscheduled assessments may be performed, particularly around the surgery if no onset of block is noted on the last scheduled assessment prior to surgery.

Onset of sensory block (sciatic and saphenous nerve tracked independently) will be defined as the earliest timepoint with loss of EITHER light touch sensation OR cold sensation in EITHER proximal OR distal locations at any time. If onset time is not achieved, it will be considered censored at the last onset assessment time prior to surgery. **Offset of sensory block** (sciatic and saphenous nerve tracked independently) will be defined as recovery of BOTH light touch

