Onset of motor block will be defined as the earliest timepoint with 2-point score of 1- Partial or no foot movement as opposed to 0- Complete foot movement. If subject does not experience loss of motor, their onset will be censored at their last available motor assessment time point prior to surgery. **Offset of motor block** will be defined as resolution of motor block at foot, first time point of the two consecutive recovery assessments (score 0- complete foot movement) (excluding Not Done assessment). If offset time is not achieved, it will be considered censored at the last offset assessment time after surgery. After offset of motor block is noted (on 2 consecutive assessments), no subsequent assessments will be required. If the patient's motor block is recovered at the last assessment to confirm, the motor block is considered recovered at this last time point. **Duration of motor block** will be defined as time between onset and offset of motor block. The censoring and missing data rule for the duration of sensory block also applies to the duration of motor block.

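### Motor-block onset and offset ignore the predose rating, so a subject with a lasting predose movement deficit is censored as still blocked after the block has resolved; the sensory reference level is also unstated

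*Protocol*

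**What the plan says.** **Predose rating.** Sensory and motor function are rated before the block in Cohort 1 (protocol 13.2.3 and Table 2). SAP section 5 defines baseline as the last measurement before study drug.

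**When testing stops.** There are two statements.
- Relative to predose: testing continues to 168 h "or until full sensory/motor function has returned to predose levels in two consecutive evaluations" (protocol 13.4). Protocol 12.7, Appendices 3 and 4, and SAP 6.3.1 and 6.3.2 say the same in similar terms.
- Relative to offset: "Once offset of sensory and motor block are determined (in two consecutive evaluations), no subsequent assessments will be conducted" (protocol Table 2, footnote b). Protocol 12.7 and SAP 6.3.1 and 6.3.2 also stop testing once offset has been noted on two assessments.

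**Motor onset and offset.** The protocol states: "Onset of motor block (sciatic) will be defined as the earliest timepoint with partial or no foot movement". Offset is "resolution of the motor block with complete foot movement on two consecutive assessments" (12.7). In SAP 6.3.2 onset is the "earliest timepoint with 2-point score of 1- Partial or no foot movement as opposed to 0- Complete foot movement", and offset is dated to the "first time point of the two consecutive recovery assessments (score 0- complete foot movement"). None of these refers to the predose score.

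**Sensory onset and offset.** SAP 6.3.1 defines onset, for each nerve, as the "earliest timepoint with loss of EITHER light touch sensation OR cold sensation in EITHER proximal OR distal locations at any time". Offset needs recovery of both modalities at both locations, twice in a row. Each rating is a yes/no answer on whether the test area feels the same as the other leg (protocol Appendix 4).

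**If offset is not reached.** Motor duration is censored at the last offset assessment after surgery (SAP 6.3.2) and treated as right censored (SAP 9.5.2.4). Missing motor assessments in the by-timepoint table are filled by last observation carried forward (SAP 9.7.2).

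**The concern.** The stopping rule in 13.4 is relative and the motor endpoint is absolute. They describe the same event only when predose function is normal. The motor scale puts partial and absent movement in one category, so a partial deficit before the block looks the same as a full block after it. No eligibility criterion concerns foot movement.

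Motor-block duration, EXPAREL versus admix in Cohort 1, is the fourth secondary endpoint and the last step of the test hierarchy (SAP 9.5). Onset and duration of both blocks are the stated pharmacodynamic endpoints. A block that has resolved but is recorded as censored pushes the Kaplan-Meier median up, and carrying the last score forward overstates the share of subjects still blocked.

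**Working it through.** The documents give no figure for motor-block duration or for predose deficits, so there is no stated result to reproduce. The check applies the written rules to one subject and then looks at size under assumed rates.

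**1. One subject under the written rules.** Early visits are at 0.25, 0.5, 0.75, 1, 2, 8, 12, 24 and 30 h, and the last is at 168 h (protocol Table 2). Assume the block is present from the 1 h visit and function is back to its predose state at the 24 h visit.
- Normal predose movement: onset 1 h, offset 24 h (confirmed at 30 h), duration 24 − 1 = 23 h, an event.
- Predose score of 1 that persists: the score is 1 at every visit. Onset is 0.25 h and two scores of 0 never occur.
  - If testing stops under the predose rule at 30 h, the duration is 30 − 0.25 = 29.75 h, censored.
  - If testing stops only at offset, it runs to the end: 168 − 0.25 = 167.75 h, censored.

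The 29.75 h figure assumes that staff can recognise the return to the predose state even though the recorded score never changes.

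**2. What the analysis does with it.** SAP 9.5.2.4 treats every censored duration as right censored, on the ground that the true duration must be longer than the one observed. Here the true duration is 23 h and the censored values are 29.75 h or 167.75 h, so that ground fails. If testing stopped at 30 h, SAP 9.7.2 carries the score of 1 forward and the subject is tabulated as blocked at each later timepoint.

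**3. Chance that someone is affected.** The comparison has 20 + 20 = 40 subjects. With an assumed rate q of lasting predose motor deficit, the chance of at least one is 1 − (1 − q)^40:
- q = 1%: 0.331
- q = 2%: 0.554
- q = 5%: 0.871

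One subject is 1/20 = 5% of an arm.

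**4. Effect on the median.** Illustrative simulation: arms of 20, the scheduled visits, log-normal duration with median 24 h and log-SD 0.6, true onset uniform from 0.1 to 1 h, 1,500 arms per setting. All inputs except the arm size and the visits are assumed. The mean Kaplan-Meier median per arm (capped at 168 h), with testing stopped by the predose rule or by the offset rule, was:

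| Assumed deficit rate | Predose rule | Offset rule |
|---|---|---|
| 0% | 27.7 h | 28.0 h |
| 2% | 28.3 h | 28.3 h |
| 5% | 29.6 h | 29.1 h |
| 10% | 30.9 h | 30.8 h |

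At 0% the two rules coincide, so the 0.3 h gap is simulation noise. The value lies above 24 h because offset is seen only at a later visit.

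**5. Sensory.** Each nerve has 2 locations × 2 modalities = 4 ratings. If the raw yes/no answers are used directly, one fixed answer of not the same gives onset and prevents offset. If each answer independently has chance q of being not the same before the block, a share 1 − (1 − q)^4 of subjects per nerve is affected: 3.9%, 7.8% and 18.5% at q = 1%, 2% and 5%. Independence is a rough assumption for four ratings on one limb.

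**The case against.** **Predose deficits should be rare.** The protocol asks for healthy adults, names diabetic neuropathy among the exclusions, and excludes inadequate foot sensation on a monofilament test. Cohort 1 is bunionectomy only. The stopping rule speaks of full function returning to predose levels, which suggests that the authors took the two as the same state. This stands as an argument for a small effect. It does not settle how a deficit is handled: no criterion covers foot movement, and three of the four sensory sites are on the lower leg.

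**Sites record onset and offset.** SAP 6.3 says these times are collected on an eCRF, so trained staff might allow for a predose deficit. That is fair, but the written motor definitions give them no basis for doing so.

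**Randomisation balances it.** A predose deficit precedes treatment, so it should be similar across arms on average. This stands. With 20 per arm, though, a single affected subject necessarily falls on one side.

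**Handling may be stated elsewhere.** Protocol 15.4 limits the pharmacodynamic set to subjects with sufficient data. The SAP text between 6.4 and section 8 was not available, so nothing is inferred from it.

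**Stronger readings.** A reader might infer that any predose deficit produces a false early onset and rules out offset for good. The documents do not support that. A deficit that clears can still meet offset, and the recorded onset is too early only if true onset comes after the first check. A reader might also infer that the sensory definitions are explicitly absolute. They are not: loss and recovery are words of change, and the protocol uses them as the SAP does. The gap is the unstated reference level.

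**Conclusion.** The motor mismatch is real. For a subject whose predose movement deficit persists, the written rules give onset at the first postdose check, no offset, and a right-censored duration even though the block has resolved. The two stopping statements agree only when predose function is normal. The sensory part is an ambiguity that becomes the same problem only if raw ratings are used directly.

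The expected effect is small. It rests on a deficit rate that the documents do not give and that the exclusions probably keep low. In the simulation the per-arm median rises by at most 28.3 − 27.7 = 0.6 h at a 2% rate and 29.6 − 27.7 = 1.9 h at 5%, with balance across arms expected. The chance that at least one of 40 subjects is affected is not a measure of bias in the comparison, and the documents do not support a claim that the test of EXPAREL against admix is biased. The change is still worth making, because a stated rule gives a wrong duration on a formally tested secondary endpoint and correcting it costs almost nothing.

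**What to change.** In protocol 12.7 and SAP 6.3.1 and 6.3.2:
- Define onset as the first worsening from the predose rating, and offset as return to the predose rating on two consecutive assessments. For sensory block, apply this by location and modality.
- Do not count a sensory location and modality already abnormal at predose toward onset or offset.
- List subjects with a predose motor score of 1 and leave them out of the motor onset and duration analysis, since the two-level score cannot show worsening from 1. The exclusion rests on a rating taken before study drug, so treatment cannot influence it.
- Reconcile the two stopping statements (13.4, 12.7, Appendices 3 and 4, Table 2 footnote b and the SAP counterparts) so that both match this definition, and carry the same wording into the onset/offset eCRF instructions.

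The cost is wording only, because the predose ratings are already collected. The downside is losing the few subjects with a predose motor deficit from the motor analysis.

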13.5. Intraoperative Procedures

- Record type of general anesthesia or sedation
- Record intraoperative drugs administered and doses
- Record date and start/end times of surgery
- Record AEs/ SAEs
- Record concomitant medications for treatment of AEs/ SAEs (if any)

13.6. Post-Anesthesia Care Unit Procedures

- Record date/time of admission to and discharge from the PACU
- For Cohort 1 only
 - Collect scheduled PK blood sample(s)
 - Perform sensory and motor function assessments
- Record AEs/ SAEs
- Record concomitant medications for treatment of AEs/ SAEs
- Subject to record NRS score (“How much pain are you experiencing now?”) upon arrival in the PACU (± 5 min); every 15 minutes while in the PACU (± 5 min); and at PACU discharge (± 5 min)

- Subject to record NRS score (“How much pain are you experiencing now?”) before administration of breakthrough pain medication
- Record date, time, and dosage of any breakthrough pain medication

13.7. Postsurgical Assessments from End of Surgery through Discharge

-
- Record pain intensity scores (NRS) (see Appendix 1, [Section 18.1](#)) measured as “How much pain are you experiencing right now?” from the end of surgery to 96 hours post-surgery as follows:
 - Every 6 hours from the end of surgery to 96 hour post-surgery, i.e., 6 h (± 2 h), 12 h (± 2 h), 18 h (± 2 h), 24 h (± 2 h), 30 h (± 2 h), 36 h (± 2 h), 42 h (± 2 h), 48 h (± 2 h), 54 h (± 2 h), 60 h (± 2 h), 66 h (± 2 h), 72 h (± 2 h), 78 h (± 3 h), 84 h (± 3 h), 90 h (± 3 h), and 96 h (± 3 h).
 - If a subject is asleep, the subject will not be awakened to assess pain. If the subject awakens within the assessment window, a pain score will be collected then.
 - Subjects will be instructed not to complete the NRS pain intensity score after any physical activity, including the motor block assessment. If that is not possible, to assess pain intensity at rest, the subject should rest quietly in a supine or seated position that does not exacerbate his or her postsurgical pain for 5-10 minutes before entering the pain score using the NRS.
 - An unscheduled NRS assessment will be obtained immediately prior to administration of any breakthrough pain medication until 96 hours post-surgery.
- Record pain intensity scores (NRS) measured as “What was your worst pain in the last 24 hours?” and “What was your average pain in the last 24 hours?”
 - Once daily at 21:00 (± 3 h) starting on POD 1.
- Subject to record satisfaction with pain management using 1 question from the International Pain Outcome (IPO) questionnaire at 96 hours (± 3 h) post-surgery.
- For Cohort 1 only:
 - Collect scheduled PK blood sample(s).
 - Perform sensory and motor function assessments.
- Record AEs/ SAEs.
- Record concomitant medications for treatment of AEs/ SAEs.

To mitigate the risk from falls, subjects will be required to be non-weight bearing for at least 2 weeks post-surgery, unless the investigator determines a limited touch down or partial weight bearing for balance with a walker assist device is more appropriate to reduce the risk of fall.

13.8. Health Care Facility Discharge

- Subjects in Cohort 1 and Cohort 2 will be discharged after the completion of the 168 h and 96 h assessments, respectively.
- Record date and time of health care facility discharge.
- Re-instruct on duties and responsibilities with the e-diary and for breakthrough medications.

13.9. Postsurgical Assessments from Discharge through POD 14

- Record pain intensity scores (NRS) measured as “What was your worst pain in the last 24 hours?” and “What was your average pain in the last 24 hours?” once daily at 21:00 (± 3 h) from the day after discharge (daily continuation from POD 1 to POD 14).

13.10. Unscheduled Visits

- If a sensory or motor function deficit persists on POD 7 (168 h post-surgery), the subject is to return for unscheduled visit(s) at the Investigator's discretion through POD 14 or until the sensory or motor function has returned to baseline, whichever occurs first.
- Record concomitant medications including all analgesic medication.
- Record AEs/SAEs and any treatment(s) for the events.

13.11. Postsurgical Day 14 Phone Call

- Remind subject to complete and return the e-diary, if applicable, after POD 14 assessment.
- Ask the subject about any new AE(s) and the resolution of any ongoing adverse event(s) since discharge. Record any adverse event information.
- Ask the subject about any medication(s) taken, that were not reported in the e-diary, since discharge from the health care facility.

